#### **8.5.1.1. US FDA-defined Snapshot Algorithm**

The analysis window at Week 48 is defined as from Study Day 295 to Study Day 378, inclusive. All HIV-1 RNA data collected on-treatment (ie, including data collected up to 1 day after the last dose date of study drug) will be used in the snapshot algorithm. Virologic outcome will be defined as the following categories:

- **HIV-1 RNA < 50 copies/mL:** this includes subjects who have the last available on-treatment HIV-1 RNA < 50 copies/mL in the Week 48 analysis window
- **HIV-1 RNA  $\geq 50$  copies/mL:** this include subjects
  - a) Who have the last available on-treatment HIV-1 RNA  $\geq 50$  copies/mL in the Week 48 analysis window, or
  - b) Who do not have on-treatment HIV-1 RNA data in the Week 48 analysis window and
    - 1) Who discontinue study drug prior to or in the Week 48 analysis window due to lack of efficacy, or
    - 2) Who discontinue study drug prior to or in the Week 48 analysis window due to reasons other than lack of efficacy and have the last available on-treatment HIV-1 RNA  $\geq 50$  copies/mL

- **No Virologic Data in the Week 48 Analysis Window:** this includes subjects who do not have on-treatment HIV-1 RNA data in the Week 48 analysis window because of the following:
  - a) Discontinuation of study drug prior to or in the Week 48 analysis window due to reasons other than lack of efficacy and the last available on-treatment HIV-1 RNA is < 50 copies/mL or,
  - b) Missing data during the window but on study drug

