2.3. Final Analysis

The final statistical analysis will be conducted after all subjects either complete the study or prematurely discontinue from the study.

This SAP describes the analysis plan for the final analysis, which will only include the all B/F/TAF analysis: safety and efficacy assessments for B/F/TAF only, not for other study drugs.

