3.2. Subject Grouping

For the all B/F/TAF analysis including extension phase, subjects will be grouped into the following groups:

- B/F/TAF group: This group includes all subjects who were randomized to B/F/TAF in the randomized phase of this study. All data from both the randomized and extension phases (if applicable) will be included.
- Stay on Baseline Regimen (SBR) to B/F/TAF group: This group includes all subjects who were randomized to continuing pre-existing regimen in the randomized phase of this study, and who then switched to B/F/TAF in the extension phase. Only data collected on and after the extension phase first dose date of B/F/TAF will be included, except that data collected **on or prior to** the extension phase first dose date of B/F/TAF will be used to derive the baseline value for the all B/F/TAF analysis.
- All B/F/TAF group: This group includes all subjects who are in the All B/F/TAF Analysis Set, which combines the two groups above.

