3.8.2. Analysis Windows

Subject visits might not occur on protocol-specified days. Therefore, for the purpose of analysis, observations will be assigned to analysis window. Since the final analysis only includes the all B/F/TAF analysis, only data included in the all B/F/TAF analysis will be assigned analysis windows.

For data listings, the observations collected from the randomized phase of the study for the subjects who were randomized to SBR group will not have analysis window assigned and will be included in listings with derived visit as blank.

The analysis windows for HIV-1 RNA, CD4+ cell count, CD4 %, hematology, chemistry, urinalysis, urine pregnancy laboratory tests, eGFR_{CG}, vital signs, and weight are presented in [Table 3-1](#).

Table 3-1. Analysis Windows for HIV-1 RNA, CD4+ cell count, CD4 %, Hematology, Chemistry, Urinalysis, and Urine Pregnancy Laboratory Tests, eGFR_{CG}, Vital Signs, and Weight

Visit ID	B/F/TAF			SBR to B/F/TAF		
	Nominal Day	Lower Limit	Upper Limit	Nominal Day	Lower Limit	Upper Limit
Baseline			1			1
Week 4	28	2	42			
Week 8	56	43	70			
Week 12	84	71	126	84	2	126
Week 24	168	127	210	168	127	210
Week 36	252	211	294	252	211	294
Week 48	336	295	378	336	295	378
Week 60	420	379	462	420	379	462
Week 72	504	463	546	504	463	546
Week 84	588	547	630	588	547	630
Week 96	672	631	714	672	631	714
Week k	k*7	(k-6)*7+1	(k+6)*7	k*7	(k-6)*7+1	(k+6)*7

The analysis windows for metabolic assessments (including fasting glucose and lipid panel: total cholesterol, high density lipoprotein [HDL], direct low density lipoprotein [LDL], triglycerides, and total cholesterol to HDL ratio) are presented in [Table 3-2](#).

Table 3-2. Analysis Windows for Metabolic Assessments

Visit ID	B/F/TAF			SBR to B/F/TAF		
	Nominal Day	Lower Limit	Upper Limit	Nominal Day	Lower Limit	Upper Limit
Baseline			1			1
Week 12	84	2	126			
Week 24	168	127	252	168	2	252
Week 48	336	253	420	336	253	420
Week 72	504	421	588	504	421	588
Week 96	672	589	756	672	589	756
Week k	k*7	(k-12)*7+1	(k+12)*7	k*7	(k-12)*7+1	(k+12)*7

The analysis windows for thyroid stimulating hormone (TSH; thyrotropin) and renal function (including urine albumin, urine creatinine, urine RBP, and urine beta-2 microglobulin, and derived ratios assessments) are presented in [Table 3-3](#).

Table 3-3. Analysis Windows for TSH, Renal Function, and HCV RNA Assessments

Visit ID	Nominal Day	Lower Limit	Upper Limit
Baseline			1
Week 24	168	2	252
Week 48	336	253	420
Week 72	504	421	588

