Week 96	672	589	756
Week k	k*7	(k-12)*7+1	(k+12)*7

The analysis windows for ECG assessments are presented in [Table 3-4](#).

Table 3-4. Analysis Windows for ECG Assessments

Visit ID	Nominal Day	Lower Limit	Upper Limit
Baseline			1
Week 24	168	2	252
Week 48	336	253	504
Week 96	672	505	756
Week k	k*7	(k-12)*7+1	(k+12)*7

3.8.3. Selection of Data in the Event of Multiple Records in an Analysis Window

Depending on the statistical analysis method, single values are required for each analysis window. For example, change from baseline by visit usually requires a single value, whereas a time to event analysis would not require one value per analysis window. When a single value is needed, the following rule(s) will be used.

If multiple nonmissing numeric observations exist in a window, then records will be chosen as follows:

- For baseline, the latest available record on or prior to the first dose date of B/F/TAF will be selected. If there are multiple records with the same collection time or no collection time recorded on the same day, average will be used for the baseline value, except for HIV-1 RNA (see below).
- For postbaseline visits:
 - For CD4+ cell count and CD4%, the record(s) collected on the latest day in the window will be selected for analysis.
 - For other numeric observations (eg, except HIV-1 RNA, CD4+ cell count, and CD4%), the record(s) collected on the day closest to the nominal day for that visit will be selected. If there are 2 days equidistant from the nominal day, the later day will be selected.
 - For any numeric observations except HIV-1 RNA, if there are multiple records on the selected day, the arithmetic mean will be used.
- For baseline and postbaseline HIV-1 RNA, the latest (considering both collection date and time) record(s) in the window will be selected. If both “HIV RNA Taqman 2.0” and “HIV RNA Repeat” (ie, the HIV-1 RNA result obtained from an additional aliquot of the original sample) are available with the same collection time, the results from the “HIV RNA Repeat” will be selected for analysis purposes; otherwise, if there are multiple “HIV RNA Taqman 2.0” records with the same collection time, the geometric mean will be taken for analysis purposes.

If multiple valid nonmissing categorical observations exist in a window, records will be chosen as follows:

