6.2.1. Analysis of CD4 Cell Count and CD4%

CD4 cell count and CD4% will be summarized using observed, on-treatment data (ie, data collected up to 1 day after the last dose date of B/F/TAF) for subjects in the All B/F/TAF Analysis Set.

The changes from baseline in CD4 cell count and CD4% at each visit will be summarized by treatment group using descriptive statistics based on observed data (ie, missing will be excluded) using the All B/F/TAF Analysis Set.

The mean and 95% CI of change from baseline in CD4 cell count over time will be plotted using observed data for the All B/F/TAF Analysis Set.

6.2.2. Analysis of the Proportion of Subjects with HIV-1 RNA < 50 copies/mL by Missing = Excluded Approach

The proportion of subjects with HIV-1 RNA < 50 copies/mL will be analyzed using the Missing = Excluded (M = E) for imputing missing HIV-1 RNA values:

In this approach, all missing data will be excluded in the computation of the percentages (ie, missing data points will be excluded from both the numerator and denominator in the computation). The denominator for percentages at a visit is the number of subjects in the All B/F/TAF Analysis Set with non-missing HIV-1 RNA value at that visit.

For M = E analysis, the number and percentage of subjects with HIV-1 RNA in the following categories will be summarized:

- < 50 copies/mL
 - < 20 copies/mL
 - < 20 Not Detectable
 - < 20 Detectable
 - 20 to < 50 copies/mL
- 50 to < 200 copies/mL
- 200 to < 400 copies/mL
- 400 to < 1000 copies/mL
- \geq 1000 copies/mL

The 95% CI of the proportion of subjects with HIV-1 RNA < 50 copies/mL within each subject group will be provided using the Clopper-Pearson Exact method.

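### The final SAP's Missing = Excluded analysis of HIV-1 RNA < 50 copies/mL has no last-dose limit, so post-treatment samples enter the B/F/TAF results and can displace the last on-treatment value

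*SAP*

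**What the plan says.** SAP 2.3 limits the final analysis to "safety and efficacy assessments for B/F/TAF only, not for other study drugs". Its HIV-1 RNA response analysis is the Missing = Excluded (M = E) analysis in 6.2.2, where the denominator at each visit is "the number of subjects in the All B/F/TAF Analysis Set with non-missing HIV-1 RNA value at that visit". The text there mentions neither the last dose nor on-treatment status.

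The data that reach 6.2.2 are set by three general rules:

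- **SAP 3.2, data included.** For subjects randomized to B/F/TAF: "All data from both the randomized and extension phases (if applicable) will be included". For SBR to B/F/TAF: "Only data collected on and after the extension phase first dose date of B/F/TAF will be included", which is a start date with no end date.
- **SAP 3.8.2, windows.** The rule is that "only data included in the all B/F/TAF analysis will be assigned analysis windows", and assignment is by study day (Table 3-1).
- **SAP 3.8.3, one record per window.** "For baseline and postbaseline HIV-1 RNA, the latest (considering both collection date and time) record(s) in the window will be selected".

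Two closely related analyses do carry a limit. CD4 in SAP 6.2.1 uses "observed, on-treatment data (ie, data collected up to 1 day after the last dose date of B/F/TAF"). The protocol's snapshot algorithm (8.5.1.1) uses "All HIV-1 RNA data collected on-treatment (ie, including data collected up to 1 day after the last dose date of study drug").

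**The concern.** HIV-1 RNA is drawn after the last study dose by design. It is on the test list of the 30-Day Follow-Up Visit (Protocol 6.6.2) and of the Early Study Drugs Discontinuation (ESDD) visit, which may fall up to 72 hours after stopping (6.6.1). Subjects who stop early are also asked to keep attending scheduled visits through Week 48 (6.4, 6.6.1).

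With no upper limit, all of these samples count as B/F/TAF results. Because the latest record in the window is chosen, a post-treatment sample does not merely sit beside the on-treatment one: it replaces it. CD4 also uses the latest record but is protected by its own limit. Other numeric tests use the day closest to nominal. HIV-1 RNA is the only latest-record measure left open.

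Snapshot analyses are not repeated in the final analysis (SAP 6.2), so M = E is the only HIV-1 RNA response result visible in it; the tertiary endpoints in 6.1.3 are redacted. Some early discontinuers who stay in the study move to a new antiretroviral regimen (Protocol Figure 6-1 note e; Appendix 6, section 4), so their later values describe that regimen. The documents do not say what subjects take at the 30-Day Follow-Up.

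**Working it through.** **Does any rule supply the limit?** The SAP writes a cut-off where it wants one: last dose + 1 day for CD4 (6.2.1) and for the last on-treatment urine albumin-to-creatinine value (7.2.5.3); last dose + 30 days for laboratory abnormalities (7.2.2) and liver tests (7.2.4); the last dose date for concomitant medication (7.4.2). Where it wants the 30-day visit ignored, in imputing a missing last dose date (3.8.1), it says so. None of these reaches 6.2.2.

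**Inputs for the day arithmetic**

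- Table 3-1 window for Week w: Day (w − 6)×7 + 1 to Day (w + 6)×7, nominal Day 7w. This reproduces the printed limits: Week 48 is 295–378 and Week 96 is 631–714.
- Extension visits: ± 6 days (Protocol 6.5.1).
- Follow-up: 30 ± 6 days after the last dose (Protocol 6.6.2), so +24 to +36 days.
- Week 48 visit: ± 6 weeks, matching the analysis window (Protocol 6.4).

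**1. Extension completers.** Assume the final visit is within ± 6 days of the nominal day and the last dose is that day.

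- Earliest follow-up: 7w − 6 + 24 = 7w + 18.
- Latest follow-up: 7w + 6 + 36 = 7w + 42.
- Upper limit of the window: (w + 6)×7 = 7w + 42.

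All 13 × 13 = 169 combinations fall in the final visit's own window, so the follow-up sample is the latest record and is selected. If the nominal visit is counted as Study Day 7w + 1, only the extreme case (7w + 43) escapes, leaving 168 of 169. Examples:

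| Group and visit | Follow-up days | Window |
|---|---|---|
| B/F/TAF, Week 96 | 690–714 | 631–714 |
| SBR to B/F/TAF, Week 48 | 354–378 | 295–378 |

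The second row also needs extension visits to be timed from the first B/F/TAF dose.

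**2. Subjects randomized to B/F/TAF who stop at Week 48.** With the visit and last dose on Day 336, follow-up is on Days 360–372, always inside 295–378. Over all 84 allowed visit days (295–378), the follow-up stays in the Week 48 window when visit day + gap ≤ 378:

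| Gap (days) | Last visit day that keeps follow-up in Week 48 | Days on which the Week 48 value is replaced | Days on which a Week 60 value is created |
|---|---|---|---|
| 24 | 354 | 60 | 24 |
| 30 | 348 | 54 | 30 |
| 36 | 342 | 48 | 36 |

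At a 30-day gap the Week 60 values fall on Days 379–408, inside the Week 60 window (379–462).

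**3. Early discontinuers.** Every scheduled visit kept after stopping gives a non-missing value in its window, and 6.2.2 counts it.

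**Not affected.** For B/F/TAF-group subjects who continue through later extension visits, the follow-up falls well after Week 48 and does not displace that value.

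**Illustration only, with assumed counts.** Suppose 220 of 225 on-treatment values are < 50 copies/mL (97.8%).

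- If 2, 5 or 10 of the 220 are replaced by a post-treatment value ≥ 50: 218/225 = 96.9%, 215/225 = 95.6%, 210/225 = 93.3%.
- If instead 10 stopped subjects are added: 230/235 = 97.9% if none is ≥ 50, down to 220/235 = 93.6% if all are.

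**The case against.** **Redaction.** M = E is neither a primary nor a secondary endpoint, and the tertiary endpoint section (SAP 6.1.3) is blacked out, so a limit could sit there. That cannot be excluded. But 6.2.2 is readable, it is where the denominator is defined, and it has no limit.

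**The 169 of 169 count is conditional.** It needs an on-schedule final visit with the last dose that day. The extension may instead end when access begins or when the sponsor stops the study in a country, which need not match a visit. For SBR to B/F/TAF it also needs visits timed from the first B/F/TAF dose, which the protocol does not state. If visits stay timed from Day 1 and the Week 48 visit falls anywhere on Days 295–378, enumeration puts the follow-up in the final visit's window in about 64% of day combinations at Weeks 72, 84 and 96 and about 66% at Week 60. This stands as a limit on the count. It does not remove the problem: the remaining follow-up samples land in a later window, still as post-treatment values.

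**Subjects may still be taking B/F/TAF at follow-up** through an access program. True, and the documents do not say. It is one reason why the direction of bias is unknown.

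**Counting every observed value is a legitimate choice,** since the protocol deliberately follows subjects after they stop. It would be, if stated as the aim. It fits poorly with a final analysis scoped to B/F/TAF alone and with the limit on CD4 in the adjacent section.

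**Small consequence.** The analysis is descriptive, with no test and no between-group comparison. This stands and bounds the importance of the point.

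**Conclusion.** The concern holds. As written, 6.2.2 with 3.2 and 3.8.3 lets post-treatment HIV-1 RNA into the B/F/TAF proportions, mainly at Week 48, Week 60 and the last extension window, and lets the scheduled follow-up sample overwrite the last on-treatment value. This is a stated set of rules producing an unintended result, not just missing detail. The day counts rest on the visit-timing assumptions given with them. How many subjects are affected, and in which direction, cannot be derived from the documents: a value after stopping may be ≥ 50 off therapy or < 50 on another regimen. The Week 48 snapshot endpoints keep their own on-treatment rule and are untouched. It should be fixed, but no primary or secondary snapshot conclusion depends on it.

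**What to change.** Add one sentence to SAP 6.2.2: only HIV-1 RNA collected up to 1 day after the last dose date of B/F/TAF is used, as in 6.2.1, and this limit is applied before the latest-record rule in 3.8.3. Keep post-treatment values in the listings. At each visit, report the number of subjects excluded because they had stopped B/F/TAF, and how many of them had an excluded value ≥ 50 copies/mL.

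The cost is one sentence, one data filter and two table rows. There is a real downside. Subjects who stopped leave the later denominators. ESDD samples taken on days 2–3 after the last dose are dropped, while those on days 0–1 stay. Some dropped values may be ≥ 50 at discontinuation, which Protocol 6.13 counts as virologic failure, so the M = E proportion could look better than it should. The second count row makes that visible. Excluding only the 30-Day Follow-Up records would keep the ESDD samples but would leave in the later visits of early discontinuers, so it repairs only part of the problem.

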6.3. Changes From Protocol-Specified Efficacy Analyses

No change from protocol-specified efficacy analysis is planned.

7. SAFETY ANALYSES

Safety data for the all B/F/TAF analysis will be summarized by treatment group and overall for the subjects in the all B/F/TAF analysis, unless specified otherwise. All safety data from the entire study including both randomized phase and extension phase will be included in data listings.

7.1. Adverse Events and Deaths

7.1.1. Adverse Event Dictionary

Clinical and laboratory AEs will be coded using the current version of MedDRA. System organ class (SOC), high-level group term (HLGT), high-level term (HLT), preferred term (PT), and lower-level term (LLT) will be provided in the AE dataset.

7.1.2. Adverse Event Severity

Adverse events are graded by the investigator as Grade 1 (mild), Grade 2 (moderate), Grade 3 (severe) or Grade 4 (life threatening) according to toxicity criteria specified in the protocol. The severity grade of events for which the investigator did not record severity will be categorized as “missing” for tabular summaries and data listings and will be considered the least severe for the purpose of sorting for data presentation.

7.1.3. Relationship of Adverse Events to Study Drug

Related AEs are those for which the investigator selected “Related” on the AE eCRF to the question of “Related to Study Treatment.” Events for which the investigator did not record relationship to study drug will be considered related to study drug for summary purposes. However, by-subject data listings will show the relationship as missing.

7.1.4. Serious Adverse Events

Serious adverse events (SAEs) will be identified and captured as SAEs if AEs met the definitions of SAE specified in the study protocol. Serious adverse events captured and stored in the clinical database will be reconciled with the SAE database from the Gilead Pharmacovigilance and Epidemiology (PVE) database before data finalization.

7.1.5. Treatment-Emergent Adverse Events

7.1.5.1. Definition of Treatment-Emergent Adverse Events

Treatment-emergent adverse events (TEAEs) are defined as 1 or both of the following:

- Any AEs with an onset date on or after the B/F/TAF start date and no later than 30 days after permanent discontinuation of B/F/TAF, or
- Any AEs leading to premature discontinuation of B/F/TAF.

7.1.5.2. Incomplete Dates

If the onset date of the AE is incomplete and the AE stop date is not prior to the first dosing date of B/F/TAF, the month and year (or year alone if month is not recorded) of onset determine whether an AE is treatment emergent.

The event is considered treatment emergent if both of the following 2 criteria are met:

- The month and year (or year) of the AE onset is **the same as or after** the month and year (or year) of the first dosing date of B/F/TAF, and
- The month and year (or year) of the AE onset is **the same as or before** the month and year (or year) of the date corresponding to 30 days after the date of the last dose of B/F/TAF

An AE with completely missing onset and stop dates, or with the onset date missing and a stop date marked as ongoing or on or after the first dosing date of B/F/TAF, will be considered as a TEAE. In addition, an AE with the onset date missing and incomplete stop date with the same or later month and year (or year alone if month is not recorded) as the first dosing date of B/F/TAF will be considered as a TEAE.

7.1.6. Summaries of Adverse Events and Death

The number and percentage of subjects who experienced at least 1 TEAE will be provided and summarized by SOC, HLT, PT, and treatment group. For other AEs described below, summaries will be provided by SOC, PT, and treatment group using the All B/F/TAF Analysis Set:

- Any Grade 2, 3, or 4 treatment-emergent AEs
- Any Grade 3 or 4 treatment-emergent AEs
- All treatment-emergent study drug-related AEs
- Any Grade 2, 3, or 4 treatment-emergent study drug-related AEs
- Any Grade 3 or 4 treatment-emergent study drug-related AEs
- All treatment-emergent SAEs
- All treatment-emergent study drug-related SAEs
- All treatment-emergent AEs that caused premature discontinuation from study drug

A brief, high-level summary of AEs described above will be provided by treatment group and by the number and percentage of subjects who experienced the above AEs. Treatment-emergent deaths observed in the all B/F/TAF phase will be also included in this summary.

Treatment-emergent death refers to deaths that occurred between the first and last dose date of B/F/TAF plus 30 days (inclusive).

Multiple events will be counted only once per subject in each summary. Adverse events will be summarized and listed first in alphabetic order of SOC and HLT within each SOC (if applicable), and then by PT in descending order of total frequency within each SOC. For summaries by severity grade, the most severe grade will be used for those AEs that occurred more than once in an individual subject during the study.

In addition to the above summary tables, all TEAEs, Grade 3 or 4 TEAEs, treatment-emergent study drug-related AEs, Grade 2, 3, or 4 treatment-emergent study drug-related AEs, and treatment-emergent SAEs will be summarized by PT only, in descending order of total frequency.

Data listings for all AEs regardless of the study phases will be provided for the following:

- All AEs
- Grade 3 and 4 AEs
- SAEs
- Study-Drug-Related SAEs
- Deaths report
- AEs leading to premature discontinuation of study drug

